### 10.1 Antitumor Effect– Solid Tumors

Response and progression will be evaluated in this study using the new international criteria proposed by the RECIST 1.1.

#### 10.1.1 Definitions

Evaluable for Target Disease Response. Only those participants who have measurable disease present at baseline, have received at least one cycle of therapy, and have had their disease re-evaluated will be considered evaluable for target disease response. These participants will have their response classified according to the definitions stated below. Note: Participants who exhibit objective disease progression or die prior to the end of cycle 1 will also be considered evaluable.

CONFIDENTIAL

This document is confidential. Do not disclose or use except as authorized.

Evaluable for Non-Target Disease Response. Participants who have lesions present at baseline that are evaluable but do not meet the definitions of measurable disease, have received at least one cycle of therapy, and have had their disease re-evaluated will be considered evaluable for non-target disease response. These participants will have their response classified according to the definitions stated below. (Note: Participants who exhibit objective disease progression or die prior to the end of cycle 1 will also be considered evaluable.)

#### 10.1.2 Disease Parameters

Measurable disease. Measurable disease is the presence of at least one (1) lesion that can be accurately measured in at least one dimension with longest diameter  $\geq 20$  millimeters (mm) using conventional techniques (CT, MRI, x-ray) or  $\geq 10$  mm with spiral CT scan. Measurable lesions must be at least 2 times the slice thickness in mm. All tumor measurements must be recorded in millimeters (or decimal fractions of centimeters). Ultrasound cannot be used to measure lesions. A lesion in a previously irradiated area is not eligible for measurable disease unless there is objective evidence of progression of the lesion prior to study enrollment. Lesions in previously irradiated areas must be clearly identified as such.

Malignant lymph nodes. To be considered pathologically enlarged and measurable, a lymph node must be  $\geq 15$  mm in short axis when assessed by CT scan (CT scan slice thickness recommended to be no greater than 5 mm). At baseline and in follow-up, only the short axis will be measured and followed.

Non-measurable disease. All other lesions (or sites of disease), including small lesions (longest diameter  $< 10$  mm) or pathological lymph nodes with  $\geq 10$  to  $< 15$  mm short axis, are considered non-measurable disease. Leptomeningeal disease, ascites, pleural/pericardial effusions, lymphangitis cutis/pulmonis, inflammatory breast disease, abdominal masses identified by physical exam that are not measurable by reproducible imaging techniques, and cystic lesions are all considered non-measurable.

Target lesions. All measurable lesions up to a maximum of 2 lesions per organ and 5 lesions in total, representative of all involved organs, should be identified as target lesions and recorded and measured at baseline. Lesions must be accurately measured in 1 dimension with a minimum size of 10 mm by CT or MRI (slice thickness no greater than 5 mm), 20 mm by chest x-ray. Nodes must have a short axis  $\geq 15$  mm. The short axis should be included in the sum of the lesions in the calculation of response. Nodes that shrink to  $< 10$  mm are considered normal. Target lesions should be selected on the basis of their size, be representative of all the involved organs, and should be lesions that can be followed with reproducible repeated measurements.

CONFIDENTIAL

This document is confidential. Do not disclose or use except as authorized.

Lytic bone lesions or mixed lytic-blastic lesions, with identifiable soft tissue components, that can be evaluated by cross sectional imaging techniques such as CT or MRI can be considered target lesions if the soft tissue component meets the definition of measurability as defined above. Cystic lesions thought to represent cystic metastases can be considered as target lesions. However, if non-cystic lesions are present, these are preferred for selection as target lesions. Lesions in previously irradiated areas or areas subject to other loco-regional therapy are usually not considered measurable unless there has been demonstrated progression of that lesion.

Non-target lesions. All other lesions, including small lesions < 10 mm or pathological lymph nodes measuring  $\geq 10$  mm to < 15 mm in short axis, as well as truly non-measurable lesions, which include leptomeningeal disease, ascites, pleural or pericardial effusion, inflammatory breast disease, lymphangitic involvement of skin or lung, abdominal masses identified by physical exam that are not measurable by reproducible imaging techniques.

#### 10.1.3 Methods for Evaluation of Disease

All measurements should be taken and recorded in metric notation, using a ruler, calipers, or digital measurement tool. All baseline evaluations should be performed as closely as possible to the beginning of treatment and never more than 4 weeks before the beginning of the treatment.

The same method of assessment and the same technique should be used to characterize each identified and reported lesion at baseline and during follow-up. Imaging-based evaluation is preferred to evaluation by clinical examination when both methods have been used to assess the anti-tumor effect of a treatment.

Clinical lesions. Clinical lesions will only be considered measurable when they are superficial (e.g., skin nodules and palpable lymph nodes) and  $\geq 10$  mm in diameter as assessed using calipers. For the case of skin lesions, documentation by color photography, including a ruler to estimate the size of the lesion, is recommended.

Chest x-ray. Lesions on chest x-ray are acceptable as measurable lesions when they are clearly defined and surrounded by aerated lung; however, CT is preferable.

Conventional CT and MRI. These techniques should be performed with cuts of 10 mm or less in slice thickness contiguously. Spiral CT should be performed using a 5 mm contiguous reconstruction algorithm. This applies to tumors of the chest, abdomen, and pelvis. Head and neck tumors and those of extremities usually require specific protocols.

CONFIDENTIAL

This document is confidential. Do not disclose or use except as authorized.

Tumor markers. Tumor markers alone cannot be used to assess response. The following parameters will be recorded on a monthly basis:

- PSA decline will be measuring according to revised PCWG-2 (2008) criteria.
- PSA changes will be recorded on all participants.
- TTPP will be based on revised PCWG-2 (2008) criteria.
- The maximal decline in PSA for each participant will be recorded for each participant.
- The date of the maximal PSA decline (nadir date) will be recorded for each participant, as will the duration from the start of therapy to the nadir PSA.

#### 10.1.4 Response Criteria

##### 10.1.4.1 Evaluation of Target Lesions

Complete Response (CR): Disappearance of all target lesions. Any pathological lymph node must have reduction in short axis to < 10 mm.

Partial Response (PR): At least a 30% decrease in the sum of the diameters of target lesions, taking as reference the baseline sum diameters.

Progressive Disease (PD): At least a 20% increase in the sum of the diameters of target lesions, taking as reference the smallest sum on study with at least a 5 mm absolute increase in the sum of all lesions. The appearance of one or more new lesions\* denotes disease progression.

Stable Disease (SD): Neither sufficient shrinkage to qualify for PR nor sufficient increase to qualify for PD, taking as reference the smallest sum diameters while on study.

Unknown (UN): Assessment of target lesions cannot be made due to insufficient or unevaluable data. In this case, a concise explanation must be given.

**Note:** If tumor response data is missing for target lesions, the overall assessment must be UN unless there is new disease that would result in an overall assessment of PD. However, if there is missing or unevaluable data for non-target lesions, but data is available for all target lesions, the overall response for that time point will be assigned based on the sum LD of all target lesions. Additionally, the assessment of CR cannot be made if there is missing or unevaluable data for non-target lesions. In this case, the overall assessment would be PR.

CONFIDENTIAL

This document is confidential. Do not disclose or use except as authorized.

**\*Definition of New Lesion:** The finding of a new lesion should be unequivocal (i.e. not due to difference in scanning technique, imaging modality, or findings thought to represent something other than tumor (ex: new bone lesions may be healing or flare of pre-existing lesions). However, a lesion identified on a follow-up scan in an anatomical location that was not scanned at baseline is considered new and will indicate PD. If a new lesion is equivocal (because of small size, etc.), follow-up evaluation will clarify if it truly represents new disease and if PD is confirmed, progression should be declared using the date of the initial scan on which the lesion was discovered.

#### 10.1.4.2 Evaluation of Non-Target Lesions

Complete Response (CR): Disappearance of all non-target lesions and normalization of tumor marker level. All lymph nodes must be non-pathological in size (< 10 mm short axis).

**Note:** If tumor markers are initially above the Institutional ULN normal limit, they must normalize for a subject to be considered in complete clinical response.

Non-CR/Non-PD: Persistence of one or more non-target lesions and/or maintenance of tumor marker level above the normal limits.

Progressive Disease (PD): Appearance of one or more new lesions and/or unequivocal progression of existing non-target lesions.

When the participant also has measurable disease, to achieve ‘unequivocal progression’ on the basis of the non-target disease, there must be an overall level of substantial worsening in non-target disease such that, even in presence of SD or PR in target disease, the overall tumor burden has increased sufficiently to merit discontinuation of therapy. A modest ‘increase’ in the size of one or more non-target lesions is usually not sufficient to qualify for unequivocal progression status. The designation of overall progression solely on the basis of change in non-target disease in the face of SD or PR of target disease will therefore be extremely rare. When the participant has only non-measurable disease, worsening in non-target disease cannot be easily quantified. A useful test that can be applied when assessing non-targets for unequivocal progression is to consider if the increase in overall disease burden based on the change in non-measurable disease is comparable in magnitude to the increase that would be required to declare PD for measurable disease: i.e. an increase in tumor burden representing an additional 73% increase in ‘volume’

CONFIDENTIAL

This document is confidential. Do not disclose or use except as authorized.

(which is equivalent to a 20% increase diameter in measurable lesions), an increase in pleural effusion from ‘trace’ to ‘large’, an increase in lymphangitic disease from ‘localized’ to ‘widespread’.

Unknown (UN): Assessment of non-target lesions cannot be made due to insufficient or unevaluable data. In this case, a concise explanation must be given.

**\*Definition of New Lesion**: The finding of a new lesion should be unequivocal (i.e. not due to difference in scanning technique, imaging modality, or findings thought to represent something other than tumor (ex: new bone lesions may be healing or flare of pre-existing lesions). However, a lesion identified on a follow-up scan in an anatomical location that was not scanned at baseline is considered new and will indicate PD. If a new lesion is equivocal (because of small size, etc.), follow-up evaluation will clarify if it truly represents new disease and if PD is confirmed, progression should be declared using the date of the initial scan on which the lesion was discovered.

#### 10.1.4.3 Evaluation of Best Overall Response

The best overall response is the best response recorded from the start of the treatment until disease progression/recurrence (taking as reference for progressive disease the smallest measurements recorded since the treatment started). The participant's best response assignment will depend on the achievement of both measurement and confirmation criteria.

#### For Participants with Measurable Disease (i.e., Target Disease)

Target Lesions	Non-Target Lesions	New Lesions	Overall Response	Best Overall Response for when Confirmation is Required:
CR	CR	No	CR	≥4 wks confirmation
CR	Non-CR/Non-PD	No	PR	≥4 wks confirmation
CR	Not evaluated	No	PR	
PR	Non-CR/Non-PD/Not evaluated	No	PR	
SD	Non-CR/Non-PD/Not evaluated	No	SD	Documented at least once ≥4 wks from baseline
PD	Any	Yes or No	PD	No prior SD, PR or CR
Any	PD*	Yes or No	PD	
Any	Any	Yes	PD	

CONFIDENTIAL

This document is confidential. Do not disclose or use except as authorized.

\* In exceptional circumstances, unequivocal progression in non-target lesions may be accepted as disease progression.

Note: Participants with a global deterioration of health status requiring discontinuation of treatment without objective evidence of disease progression at that time should be reported as "*symptomatic deterioration*". Every effort should be made to document the objective progression even after discontinuation of treatment.

**For Participants with Non-Measurable Disease (i.e., Non-Target Disease)**

Non-Target Lesions	New Lesions	Overall Response
CR	No	CR
Non-CR/non-PD*	No	Non-CR/non-PD*
Not all evaluated	No	Not evaluated
Unequivocal PD	Yes or No	PD
Any	Yes	PD
*Non-CR/non-PD is preferred over stable disease for non-target disease since SD is increasingly used an endpoint for assessment of efficacy in some trials so to assign this category when no lesions can be measured is not advised.		

10.1.5 Duration of Response

Duration of overall response: The duration of overall response is measured from the time measurement criteria are met for CR or PR (whichever is first recorded) until the first date that recurrence or progressive disease (PD) is objectively documented, taking as reference for PD the smallest measurements recorded since the treatment started, or death due to any cause. Participants without events reported are censored at the last disease evaluation.

Duration of overall complete response: The duration of overall CR is measured from the time measurement criteria are first met for CR until the first date that recurrent or progressive disease is objectively documented, or death due to any cause. Participants without events reported are censored at the last disease evaluation.

Duration of stable disease: Stable disease is measured from the start of the treatment until the criteria for progression are met, taking as reference the smallest measurements recorded since the treatment started.

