## 5.5 Duration of Follow-Up

Participants will be followed for up to 5 years post-study discontinuation or until death, whichever comes first. Participant follow up visits will be at the research clinic for the first 2 years of follow-up. Following the first 2 years, participant follow-up can be done via medical record review and/or by phone. Participants will be followed for subsequent lines of therapy, including line of agent, name of agent, and PSA kinetics following study drug discontinuation and correlate with response to study drug. This information will be updated every 6 months. The research team will collect this information during patient clinic visits, by phone, or via medical record review.

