**Number of Subjects/Study Duration:**

We plan to enroll a total of 66 participants to obtain 40 evaluable participants. Assuming an accrual rate of 6 participants per month, enrollment will take 11 months. Participants will be treated with enzalutamide 160 mg orally per day. We will assess PSA at baseline and day 1 of each 28-day cycle until radiographic progression defined by PCWG2. Participants will continue on therapy until radiographic or symptomatic progression or taken off study for another reason.

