**14.2 Analysis of Secondary Endpoints**

Safety and tolerability of enzalutamide will be evaluated. All participants who receive at least 1 dose of study drug will be included in these analyses. A summary of all Grade 1-4 treatment-related toxicities will be provided by toxicity type and maximum grade. The maximum grade consolidates the reports of a given type of toxicity for a participant over time by taking the maximum grade across time (i.e. a participant appears only once for a given type of toxicity). Participants with reports of multiple toxicities of different types are reported multiple times under the relevant toxicity categories. ‘Treatment-related’ toxicities are defined by an attribution as possible, probable or definite. With 66 participants, the maximum width of a 90% CI for a given toxicity rate is 22%. The probability of observing at least one rare severe toxicity (true rate=5%) is 95%. The number of cycles completed with and without dose modifications and treatment delays.

PSA response to enzalutamide will be summarized as frequency and percent. Participants who are unevaluable for response will be included in the denominator as nonresponders when calculating the response rate. Duration of PSA response for the regimen of enzalutamide will be defined relative to the first achievement of PSA response and will be estimated using the method of Kaplan and Meier. PSA response will be measured according to PCWG2 (2008) criteria.

Participants with measurable disease will be evaluated for response using RECIST 1.1 criteria. Duration of response of bone lesions or measurable disease will be described using Kaplan-Meier estimates.

The set of AR resistance measures will be summarized using descriptive statistics (mean, median, standard deviation (SD), interquartile range (IQR)). Correlation among measures will be assessed graphically with scatter plots and using Pearson correlation coefficients (or Spearman if appropriate).

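### Duration of response ends only at objective PD or death, with no limit on the time since the last scan, so unscanned months after treatment can be counted as response

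*Combined protocol and SAP*

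**What the plan says.** Section 10.1.5 measures overall response from the first CR or PR "until the first date that recurrence or progressive disease (PD) is objectively documented", "or death due to any cause. Participants without events reported are censored at the last disease evaluation". The definition for complete response has the same structure. Neither has a rule for stopping treatment, missed scans or new therapy. Section 14.2 adds only this: "Duration of response of bone lesions or measurable disease will be described using Kaplan-Meier estimates".

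Other sections bear on how the rule works:

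- **Stopping treatment.** Section 14.1: "Participants will continue on therapy until radiographic or symptomatic progression or taken off study for another reason". Section 5.4 also allows stopping for unacceptable AEs.
- **Imaging.** The study calendar (section 9) marks CT/MRI and bone scan at pre-study and every 12 weeks. Both rows are blank at the end-of-treatment and follow-up visits.
- **Follow-up.** Section 5.5: "Participants will be followed for up to 5 years post-study discontinuation or until death, whichever comes first". After 2 years this can be by phone or record review.
- **Symptomatic progression.** Section 10 lists it among the items used to determine progression. Section 10.1.4.3 reports deterioration without objective progression as a separate category and adds: "Every effort should be made to document the objective progression even after discontinuation of treatment".

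**The concern.** The two events that can end a response are not observed equally well. Deaths are captured for years, but no scan that could show PD is scheduled at or after the end-of-treatment visit. A responder can leave treatment for symptomatic progression or toxicity without objective PD. If none is documented later and he dies, the event is dated at death. All the time between, including time on other drugs, counts as response to enzalutamide. If no death is reported, he is censored at his last scan. For symptomatic progression that censoring is informative, because he leaves the risk set when he is failing.

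The sections also disagree on whether symptomatic progression is progression for this endpoint. Two analysts could draw different Kaplan-Meier curves from the same data for a stated secondary objective (section 1.3).

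**Working it through.** The plan gives no median, event count or precision for duration of response, so there is no figure to reproduce. The size below is an illustration.

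**One man.** Twelve weeks is 84/30.4375 = 2.76 months. Assume PR at week 12, last scan at week 24, a stop 0.5 months later without objective PD, and death at month 24.

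- Written rule: 24 − 2.76 = 21.2 months, event.
- Censored at last scan: 5.52 − 2.76 = 2.8 months.
- Stop counted as the event: 5.52 + 0.5 − 2.76 = 3.3 months.

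For death at 12 to 36 months, the written rule gives 9.2 to 33.2 months.

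**How often death is seen.** If survival is exponential with the cited median of 18.4 months (section 2.1.1), the share dying within 60 months is 1 − 2^(−60/18.4) = 89.6%. For medians of 12 and 24 months it is 96.9% and 82.3%. Most men with no documented PD would therefore have their event at death; about 3–18% would be censored at the last scan.

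**Kaplan-Meier comparison by simulation.** Inputs:

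- Median 8.3 months from response to progression. The protocol gives 8.3 months as time to PSA progression (2.1.1) and as treatment duration (6.1.1), in all treated men.
- 16% stopping first for an AE (6.1.1, cited phase 3 trial).
- Median survival after stopping 18.4 − 8.3 = 10.1 months. This is a difference of medians and only a rough guide.
- Exponential times, objective PD dated at the next 12-week scan, 60 months of follow-up.
- Symptomatic-only share of progressions 10–30%, assumed; the documents give none.
- No objective PD documented later in any man who stops without it.

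The share of responders without objective PD is 0.16 + 0.84 × share, which is 24%, 33% and 41%. In these men the written rule adds about 13 months on average.

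| 12-month estimate | share 10% | 20% | 30% |
|---|---|---|---|
| Written rule | 44% | 47% | 51% |
| Symptomatic progression as event, AE stops censored at last scan | 39% | 38–39% | 38–39% |
| All such stops censored at last scan | 43% | 47% | 51% |
| Only deaths more than 24 weeks after last scan censored | 40% | 42% | 45% |

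At a 5% share, the gap between the first two rows is about 2–3 points. Without AE stops, the written rule gives 43%, 47% and 51%, so nearly all of the gap comes from symptomatic progression.

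**Medians over a wider range.** With median time to PD 6–12 months, 10–40% stopping first and post-stop median survival 8–18.4 months, the written-rule median minus the stop-as-event median runs from 0 to about +5.5 months. Minus the censor-at-last-scan median, it runs from about −2.8 to +2.8 months.

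**The case against.** **Objective PD may still be documented.** Section 10.1.4.3 asks for this after symptomatic deterioration, and a PD date would end the response before death. The calendar's 12-week column is not labelled as on-treatment only, and section 5.6 keeps men with unacceptable AEs on study until the AE resolves. This stands in part: some men will be scanned, and the simulation gives these provisions no effect, so it leans high. But the instruction schedules no scan and does not cover toxicity stops, and PD found later may be dated after time on another drug.

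**The death rule is not the main driver.** Censoring every such stop at the last scan gives almost the same curve as the written rule. That is right, and it shows that censoring alone does not solve the problem: for symptomatic progression the censoring is informative. Limiting late deaths does lower the estimate, to 40–45%, but most of the remaining gap depends on how symptomatic progression is classified.

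**That classification is a choice of endpoint.** RECIST 1.1 is the stated standard, and symptomatic progression is less objective than imaging. This is fair, and is why both versions should be reported.

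**Responders may be few.** In the cited phase I/II study 59 of 140 men (42%) were assessed for soft-tissue response. Then 66 × 0.42 ≈ 28 men, and at response rates of 22–29% about 6–8 responders. If all 66 were measurable, 66 × 0.29 ≈ 19. With 8 responders the 95% half-width around 39% is 1.96 × √(0.39 × 0.61/8) ≈ 34 points; with 19, about 22. A shift of 5–12 points is well inside that. This stands and limits the importance of the point, but it does not make the rule correct.

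**Conclusion.** The concern holds for the rule as written. It counts unscanned months after treatment as response for a man who stops without objective PD, has none documented later and dies. Sections 10, 10.1.4.3 and 10.1.5 also conflict on symptomatic progression. Under the assumptions shown, the 12-month estimate is about 5–12 points higher than with symptomatic progression as an event, and 2–3 points at a 5% share. None of the inputs is specific to responders, and the symptomatic-only share has no source in the documents.

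Three stronger readings are not supported:

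- A reader might infer that every responder who stops without PD is scored as responding until death. That needs both no later documented PD and an observed death; otherwise the PD date or the last scan applies.
- A reader might infer that the estimate is always biased upward. Against censoring at the last scan, the median can move either way or not at all, and toxicity stops alone add almost nothing to the 12-month figure.
- A reader might infer that the trial's main result is at risk. Duration of response is descriptive and secondary, with no test or sample-size role, and the primary analysis is unaffected.

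**What to change.** For the analysis only, amend section 10.1.5 (both duration definitions) and refer to it from 14.2:

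1. Count a death as the end of response only if it falls within two scan intervals (24 weeks) of the last disease evaluation; otherwise censor at that evaluation.
2. Censor a man who stops for a reason other than progression, with no objective PD or counted death, at his last disease evaluation.
3. Reconcile sections 10, 10.1.4.3 and 10.1.5 on symptomatic progression. Report duration of response both with it as an event, dated from the Off Treatment form, and with it not as an event.
4. Keep the current definition as a sensitivity analysis.

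Add censoring at new therapy only if its start date is collected. Section 5.5 lists line of agent, name of agent and PSA kinetics, updated every 6 months, but no start date.

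The cost is wording. The reason and date of removal (5.6), the Off Treatment form and the survival form (12.1.2) are already planned. The reported duration will be somewhat shorter, the 24-week limit is a convention to be fixed before analysis, and symptomatic progression brings in a less objective event.
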